3.2.2 SECONDARY

OBJECTIVES	ENDPOINTS	JUSTIFICATION FOR ENDPOINTS
Secondary		

OBJECTIVES	ENDPOINTS	JUSTIFICATION FOR ENDPOINTS

 • To compare, between the same two groups over the same time period, 
 1) The rate of self-reported new episodes of respiratory illness (URI or ILI), DIA and UFI. 2) The rate of self-reported new episodes of 
 a) ILI b) URI c) DIA d) UFI 3) The rate of clinically-confirmed episodes of the study syndromes 4) The rate of laboratory-confirmed episodes of the study syndromes • First event, per protocol analysis (receipt of all 3 doses) and extended per protocol analysis (receipt of at least one dose) of primary endpoint and secondary endpoints 1-7 (primary analyses will focus on all events and intention-to-treat analyses). • Sub-group analyses for potential effect measure modification of Primary Endpoint and Secondary Endpoints 1-7 by 
 1) Sex (males or females) 2) Season (spring = January cohorts; summer = May cohorts; winter = September cohorts) 	
 1. Number of self-reported new episodes of respiratory illness (URI or ILI), DIA and UFI. 2. Number of self-reported new episodes of URI 3. Number of self-reported new episodes of ILI 4. Number of self-reported new episode of DIA 5. Number of self-reported new episodes of UFI 6. Number of clinically-confirmed episodes of the study syndromes, defined as an episode resulting in a visit to the RUSVM Student Health Services with a recorded ICD10 of J00 (acute nasopharyngitis); J11 (influenza due to unidentified influenza virus); R19.7 (diarrhea) or R50.9 (fever, unspecified). 7. Number of laboratory-confirmed episodes of the study syndromes, defined as clinically-confirmed episodes with laboratory diagnosis of influenza virus, respiratory syncytial virus or metapneumovirus (URI/ILI episodes) or rotavirus or norovirus (DIA episodes) . 	
For Secondary Endpoint 1, in any week a single participant could report one of the following:
 
 • No CID episode • One CID episode (URI or ILI or DIA or UFI) • Two CID episodes (either URI or ILI, and DIA) 
By this definition, a participant cannot experience more than two CID episodes within a week, as occurrence of URI together with ILI is considered an episode of ILI only, and occurrence of URI, ILI and/or DIA precludes the occurrence of UFI.
 
We also will attempt to determine impact on etiologically confirmed outcomes but we expect few episodes to meet this criteria and thus study power will be low. Etiological confirmation will be done for a limited range of pathogens only (influenza virus, respiratory syncytial virus, metapneumovirus, rotavirus and norovirus) through an independent research protocol (RUSVM IRB protocol #17-11-FL) and the test results sent back to the RUSVM Student Health Services.


OBJECTIVES	ENDPOINTS	JUSTIFICATION FOR ENDPOINTS

3) Class (new arrivals [VP and 1st semester] vs. 5th semester)
 
 Subset analyses of Primary Endpoint and Secondary Endpoints 1-7 in the subset of participants excluding those participants categorized as immunosuppressed (reporting use of immunosuppressive medications or treatments or occurrence of immunosuppressive medical conditions in baseline questionnaire) 		

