
subjects that receive at least one dose of a three-dose course of rabies vaccine and those subjects that receive a placebo injection.
 
Primary analysis will be based on an intention-to-treat analysis.
	
or undifferentiated febrile illness (UFI).
 
URI is defined as (two or more of the following: runny or blocked nose/sneezing/sore throat/cough) and (absence of itchy or watery eyes).
 
ILI is defined as [fever (feeling feverish, or an axillary, oral or otic temperature of 100°F or higher)] and (cough or sore throat).
 
DIA is defined as three or more loose stools within a 24-hour period.
 
UFI is defined as [fever (feeling feverish, or an axillary, oral or otic temperature of 100°F or higher)] and (not meeting the case definition of URI, ILI or DIA).
 
To be defined as a new episode, illness must be preceded by at least one week without any CID.
 
Time Frame: Weekly self-reporting of occurrence or non-occurrence of episodes of CID for a maximum of 26 weeks, starting 10-14 days after allocation.
	
undifferentiated febrile illness, and therefore there is no need to separate those outcomes, and no biological basis currently for doing so. If rabies vaccine acts non-specifically to prevent some infectious diseases, its biological basis is unknown. However, the only existing data suggest it may work as a T-cell enhancer, which in theory could prevent any infectious disease.
 
Assessment of occurrence of study syndromes will be done on a weekly basis, through completion of a weekly survey of self-reported symptoms of illness by participants. For the composite outcome of CID, a week without any illness must occur before an illness is considered a new episode; a similar requirement will exist within individual disease syndromes.

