8 SAMPLE SIZE

The estimated number of participants needed to achieve the study's primary objective is 430 (215 in each group). The sample size was calculated using the approach for comparing two negative binomial rates based on true rates (Approach 2 in [17]), implemented using the function *power.nb.test* in package 'MKmisc' in R, and assuming the following parameter values:

- Alpha level = 0.05
- Targeted power = 0.8
- Event rate for control group = 2 (expected mean number of new CID episodes [composite primary endpoint] over 26 weeks)
- Rate ratio under alternative hypothesis = 0.75
- Average length of participation (accounting for drop-out and non-response) = 21 weeks (0.8 of 26-week observation period)
- Negative binomial dispersion parameter (k in [17]) = 0.4

The three nuisance parameters (average length of participation, event rate for control group and negative binomial dispersion parameter) were estimated from data collected over 7 weeks of a pilot study of rates of CID episodes in 90 RUSVM students (40 in 1st semester and 50 in 5th semester) from 21 May to 8 July, 2018 (weeks 3 through 9 of summer semester).

An internal pilot study will be done using data from the first 300 participants to complete the study. As the expected enrollment rate is <100 participants per semester, this will allow capture of seasonal variation in event rates (≥ 3 semesters in internal pilot study). The three nuisance parameters will be re-estimated from the internal pilot study data and the sample size recalculated, using a blinded sample size re-estimation method for count data [18, 19], which maintains required power without an increase in the type I error. The sample size will only be increased and not decreased on the basis of the internal pilot study (that is, if the recalculated sample size is smaller than the original sample size, the original sample size will still be used).

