14 STATISTICAL METHODS

The analysis of the primary endpoint and secondary endpoints 1-7 will be conducted after all randomized participants have completed the study (one week after receipt of the final weekly survey) or have withdrawn from the study, whichever occurs first. Primary analysis will be based on intention-to-treat analysis of all events (that is, not just occurrence of first events). The comparison of incidence rates of CID episodes (primary endpoint and secondary endpoints 1-7) between the treatment arms will be performed using a negative binomial regression model, which accounts for different lengths of observation period. Participants' number of CID episodes will be modelled as a function of treatment group, with the number of weeks of observation included as an offset in the model. This analytic model estimates the rate ratio, λ_t / λ_c , which quantifies the risk of CID episodes associated with rabies vaccination (λ_t) in comparison to placebo injection (λ_c). Statistical significance will be controlled at the 2-sided, 0.05 alpha level, and the estimated rate ratio compared with 1, assuming the following statistical hypothesis:

H_0 (null hypothesis): Rate ratio = 1

H_1 (alternative hypothesis) Rate ratio $\neq 1$

Treatment effect will be based on the coefficient in the model. Statistical significance at the pre-specified alpha level will be based on a Wald testing procedure. CID rates (primary

endpoint and secondary endpoints 1-7) for rabies vaccine and placebo, and the rate ratio, will be presented and will include 95% confidence intervals.

A detailed description of the statistical methods that will be used for the primary and secondary endpoints will be provided in a Statistical Analysis Plan (SAP).

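### Secondary syndrome endpoints can count one continuous illness twice, or under two syndromes, when its weekly label changes; the primary endpoint is not affected

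*Combined protocol and SAP*

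**What the plan says.** Section 3.2.1 defines URI, ILI, DIA and UFI from symptoms in a weekly survey. The URI definition does not exclude fever. UFI is residual: fever that meets none of the other three definitions. For the primary composite, a new episode needs a preceding week free of any CID. For single syndromes the section adds only that "a similar requirement will exist within individual disease syndromes".

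Section 3.2.2 lists five self-reported secondary endpoints. Endpoint 1 covers respiratory illness (URI or ILI taken together), DIA and UFI. Endpoint 2 is "Number of self-reported new episodes of URI", and Endpoints 3, 4 and 5 do the same for ILI, DIA and UFI. The justification column, in a paragraph introduced for Endpoint 1, sets the within-week hierarchy: "occurrence of URI together with ILI is considered an episode of ILI only, and occurrence of URI, ILI and/or DIA precludes the occurrence of UFI".

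Section 14 leaves the detailed statistical methods to an SAP. The document reviewed contains no separate SAP text and no text of the weekly survey (Appendix G).

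**The concern.** The hierarchy works within a week and the gap works within a syndrome, so neither governs an illness that changes label between weeks. Such changes are to be expected. Loss of fever alone can turn an ILI week into a URI week, and a fever that starts on the last day of a survey week can be UFI in one survey and ILI in the next.

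Endpoints 2 to 5 are there to show which syndromes respond. If the convalescent week of an ILI enters the URI count, an effect confined to ILI shows up in part as an effect on URI. If a prodromal fever counts separately, Endpoints 1 and 5 contain episodes that are not distinct illnesses. The same counts feed the first-event, per-protocol, subgroup and subset analyses in section 3.2.2 and the exploratory analyses in section 3.2.3.

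**Working it through.** **Planning figure.** Section 8 states a size only for the primary endpoint. Inputs: two-sided alpha 0.05, power 0.8, control rate 2 (so 1.5 under the rate ratio of 0.75), exposure 0.8, dispersion 0.4.

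n per arm = (1.960 + 0.842)² × [(1/0.8)(1/2 + 1/1.5) + 2 × 0.4] / (ln 0.75)² = 214.18, so 215 per arm and 430 in total, as stated.

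This figure rests on the composite count, which the next step shows is unaffected.

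**Counting rules applied to single unbroken illnesses.** U = URI only, B = URI and ILI criteria both met, F = UFI. Each sequence has illness-free weeks before and after it. An episode is a qualifying week not directly preceded by a week of the same kind. Endpoint 1 is shown with URI and ILI sharing one gap (pooled) and with a gap for each (separate). Endpoint 2 is shown with and without the hierarchy.

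| Weeks | Primary | Endpoint 1 pooled | Endpoint 1 separate | Endpoint 2 with / without hierarchy | Endpoint 3 | Endpoint 5 |
|---|---|---|---|---|---|---|
| F, B | 1 | 2 | 2 | 0 / 1 | 1 | 1 |
| F, U | 1 | 2 | 2 | 1 / 1 | 0 | 1 |
| F, B, F | 1 | 3 | 3 | 0 / 1 | 1 | 2 |
| B, U | 1 | 1 | 2 | 1 / 1 | 1 | 0 |
| U, B, U | 1 | 1 | 3 | 2 / 1 | 1 | 0 |
| B, U, B | 1 | 1 | 3 | 1 / 1 | 2 | 0 |
| B, B | 1 | 1 | 1 | 0 / 1 | 1 | 0 |

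- The primary endpoint counts 1 in every row.
- F, B and F, U add two to Endpoint 1 under either gap reading.
- B, U puts one illness once into Endpoint 2 and once into Endpoint 3, with or without the hierarchy.
- U, B, U is counted twice in Endpoint 2 only if the hierarchy extends to that endpoint.
- B, U, B is counted twice in Endpoint 3 either way. The cause is the within-syndrome gap.

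**How often an ILI would spill into URI.** Assumptions not in the documents: onset is equally likely on each of the 7 survey days; a week with any fever day is ILI; a later week with illness but no fever is URI; and two URI symptoms without itchy or watery eyes last to the end. Counting the onset days that leave a URI week after the ILI week or weeks gives:

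| Fever (days) | Illness (days) | Share spilling over, p |
|---|---|---|
| 2 | 5 | 3/7 |
| 3 | 7 | 4/7 |
| 2 | 7 | 5/7 |
| 3 | 10 | 7/7 |

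In the first row, for example, only onsets on days 4, 5 and 6 qualify.

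**Effect on the URI rate ratio.** Assume 1.0 true URI and 0.4 ILI per participant, and a vaccine that halves ILI and leaves URI alone.

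URI rate ratio = (1.0 + 0.2p) / (1.0 + 0.4p)

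- p = 3/7: 1.086 / 1.171 = 0.93
- p = 1: 1.2 / 1.4 = 0.86

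If the vaccine multiplies both syndromes by the same factor r, the ratio is r(1.0 + 0.4p) / (1.0 + 0.4p) = r. There is then no distortion, and no effect on any syndrome (r = 1) is a special case.

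**The case against.** The strongest reply is that the text does not fix the reading. The hierarchy is introduced for Endpoint 1 and nothing extends it to Endpoints 2, 3 or 5. Endpoint 1 names URI and ILI as one respiratory category, which favours a pooled gap, and B, U then counts once there. The requirement for single syndromes is left open, and an SAP or the survey form may settle it. This all stands, and it limits the finding.

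A reader might infer that the relabelling itself makes Endpoints 1, 2, 3 and 5 all double-count. The documents do not support that:

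- Relabelling never creates or removes an ILI week, so it cannot alter Endpoint 3.
- Endpoint 5 is affected through the residual definition of UFI and the syndrome-level gap.
- One count in Endpoint 2 and one in Endpoint 3 is contamination across two separately analysed endpoints, not double counting within either.
- The hierarchy can lower the URI count, as B, B shows. Across all 27 three-week respiratory sequences (URI only, both, ILI only; unweighted), Endpoint 2 exceeds 1 in 2 with the hierarchy and in 4 without it.

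The reply does not remove the UFI transition, which adds two to Endpoint 1 even with pooled respiratory illness. Nor does it remove the spill-over into Endpoint 2. Without the hierarchy, every ILI that also meets URI enters the URI count; if all do, p = 1 and the illustrative ratio is 0.86.

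**Conclusion.** The concern holds for the secondary syndrome endpoints. With a gap applied within each syndrome to weekly labels, one continuous illness can count twice or under two syndromes. The firmest case is UFI next to ILI or URI, which adds two to Endpoint 1 and one to Endpoint 5 on either gap reading. Spill-over of ILI into Endpoint 2 follows with or without the hierarchy. The double count of U, B, U in Endpoint 2 depends on extending the hierarchy to that endpoint.

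The ratios of 0.93 to 0.86 are illustrations that rest on assumed rates, durations and symptom persistence; the documents give none of these. They show that the URI ratio is pulled toward the ILI ratio when the two effects differ. It would be too strong to infer that a URI result could not be interpreted at all, or that the rule favours one arm when the vaccine does nothing. The primary endpoint and the 430 stand. This should be corrected before unblinding, so that the counting rule is not chosen with results in view.

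**What to change.** In section 3.2.2, define the illness run first and label it second.

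- **Endpoints 1 to 3.** A new respiratory episode is a run of weeks with URI or ILI, preceded by at least one week with neither. Count it once in Endpoint 1. For Endpoints 2 and 3, label the whole run ILI if any week meets ILI, otherwise URI.
- **Endpoints 1 and 5.** A UFI week directly before or after a URI, ILI or DIA week belongs to that episode and is not counted separately. State that such a week does not break the run, and that consecutive UFI weeks leading into or out of the episode are treated alike.

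Under this rule every sequence in the table counts once in Endpoint 1 and never under both URI and ILI, and the illustrative URI ratio returns to 1.00.

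The cost is endpoint wording, matching SAP text and a few lines of derivation code, with no new data. URI and UFI counts become somewhat smaller. Two distinct back-to-back infections may be merged, which the primary endpoint's gap rule already accepts. The syndrome-by-syndrome count can be kept as a sensitivity analysis, provided its gap rule is spelled out for each endpoint.

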3.2.3 TERTIARY

OBJECTIVES	ENDPOINTS	JUSTIFICATION FOR ENDPOINTS
Tertiary/Exploratory		

 Among the vaccinated group only, to compare Primary Endpoint and Secondary Endpoints 1-7 between high responders and low responders, defined by RVNA titers measured by rapid fluorescent foci inhibition test (RFFIT) at day 180 after first vaccination. Explore latency period and duration of effect on Primary Endpoint and Secondary Endpoints 1-5. Explore the effect of dose (1 vs. 2 vs. 3) on Primary 	
 Primary Endpoint and Secondary Endpoints 1-7 Primary Endpoint and Secondary Endpoints 1-5 Primary Endpoint and Secondary Endpoints 1-5 	See above

OBJECTIVES	ENDPOINTS	JUSTIFICATION FOR ENDPOINTS
Endpoint and Secondary Endpoints 1-5.		

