3.2.5 VACCINE EFFICACY ANCILLARY STUDY

OBJECTIVES	ENDPOINTS	JUSTIFICATION FOR ENDPOINTS
Vaccine efficacy ancillary study		

 • To compare, between participants in each group over three consecutive cohorts (Spring 2019, Summer 2019 and Fall 2019)(n = ~350), concentrations of rabies virus neutralizing antibody (RVNA) before first injection (day -7) and six months after first injection (day 180). • As a secondary objective, sub-group analysis for potential effect measure modification of vaccine efficacy endpoint by sex (males or females) 	
 • Geometric mean concentration (GMC) of RVNA titers measured by rapid fluorescent foci inhibition test (RFFIT) on sera samples collected 7 days before injection (day -7) and 6 months after first injection (day 180). 	

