11 ALLOCATION

11.1 SEQUENCE GENERATION

Allocation of participants to study arms will be done by restricted randomization (permuted block design with stratification). Stratification will be by cohort (three cohorts per year: January, May and September) and sex (within cohort). Within strata, randomization will be done by computer-generated randomly permuted blocks of varying size (using the function *blockrand* in the package 'blockrand' in R). Enrolled students will be allocated in a 1:1 ratio to one of the two study arms.

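### The antibody-response analysis compares high with low responders without a stated cut-off; log titer as a continuous term would keep more information and close off the choice of cut

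*Combined protocol and SAP*

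**What the plan says.** Section 3.2.3, under the label "Tertiary/Exploratory", sets an objective "Among the vaccinated group only": "to compare Primary Endpoint and Secondary Endpoints 1-7 between high responders and low responders, defined by RVNA titers". The groups are defined in full as "high responders and low responders, defined by RVNA titers measured by rapid fluorescent foci inhibition test (RFFIT) at day 180 after first vaccination". No threshold, quantile, group share or model is given for this objective.

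The titers come from the vaccine efficacy ancillary study in Section 3.2.5, which compares the arms "over three consecutive cohorts (Spring 2019, Summer 2019 and Fall 2019)(n = ~350"). Its endpoint is "Geometric mean concentration (GMC) of RVNA titers measured by rapid fluorescent foci inhibition test (RFFIT"), so the protocol already summarises titer on the log scale. On allocation, Section 11.1 states: "Enrolled students will be allocated in a 1:1 ratio to one of the two study arms". Section 8 plans the internal pilot around a slower intake: "As the expected enrollment rate is <100 participants per semester".

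Section 14 specifies negative binomial regression with weeks of observation as an offset for the primary endpoint and secondary endpoints 1-7. It announces a separate SAP for the primary and secondary endpoints and does not mention the tertiary objectives.

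**The concern.** Titer is a continuous measurement. Splitting it into two groups treats everyone on one side of the cut as alike, which discards information unless the true relation is a step at that cut. The protocol gives no reason to expect such a step: Section 3.2.1 says the biological basis of any non-specific effect is unknown.

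The missing cut-off is a second weakness. The analysis covers eight endpoints, and nothing in the text says when or by what rule the line between high and low will be drawn. Under Section 21, the principal investigator and study coordinator have access to the full dataset, so the line could be drawn with illness outcomes in view.

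This is the only planned analysis that relates strength of antibody response to illness. A result that depends on the cut could be read as support for a biological gradient, and a real gradient could be missed because the split lacks power.

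**Working it through.** **1. The plan's own sample size.** Inputs from Section 8: control rate r0 = 2 per 26 weeks, rate ratio 0.75 (so r1 = 1.5), average participation t = 0.8 of the period, k = 0.4, two-sided alpha 0.05, power 0.80.

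n per arm = (1.960 + 0.842)² × [(1/t)(1/r0 + 1/r1) + 2k] / (ln 0.75)² = 7.849 × [1.25 × (0.5 + 0.667) + 0.8] / 0.0828 = 214.2

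This rounds up to 215 per arm, 430 in total, as stated. It also confirms how k enters the variance, which step 4 uses. The documents give no sample size or power for the responder analysis itself.

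**2. Number of vaccinees with a titer.**
- From Section 3.2.5: 350 / 2 = about 175.
- From Section 8: three cohorts of fewer than 100 give fewer than 300, so fewer than 150 vaccinees.

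The two do not agree (350 / 3 is about 117 per cohort). Neither allows for people without a day-180 sample, and the documents give no figure for that.

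**3. Information kept by a split.** Assume log titer is roughly normal and its effect on the log rate is linear. With a share p below the cut, relative efficiency is φ(z_p)² / [p(1 − p)].

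| Share low/high | Kept | Lost |
|---|---|---|
| 50/50 | 0.637 (= 2/π) | 36% |
| 40/60 | 0.622 | 38% |
| 33/67 | 0.593 | 41% |
| 25/75 | 0.539 | 46% |
| 20/80 | 0.490 | 51% |

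So 36% is the smallest loss under this model. At the median, 175 vaccinees count as 111 and 150 as 95.

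**4. Power.** Expected episodes per vaccinee: 2 × 0.75 × 0.8 = 1.2. Information per person: 1 / (1/1.2 + 0.4) = 0.811. Wald power is Φ(|ln RR| × √(n × 0.811) − 1.96) for continuous titer; for a median split, n is multiplied by 0.637.

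For n = 175 and RR 0.80 per SD: 0.2231 × √141.9 = 2.658, so power is Φ(0.698) = 76%. Split: 2.658 × 0.798 = 2.121, so power is Φ(0.161) = 56%.

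| Assumed RR per SD | n | Continuous | Median split |
|---|---|---|---|
| 0.80 | 175 | 76% | 56% |
| 0.80 | 150 | 69% | 50% |
| 0.85 | 175 | 49% | 34% |
| 0.85 | 150 | 43% | 30% |
| 0.90 | 175 | 24% | 17% |
| 0.90 | 150 | 21% | 15% |

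If only 80% gave a day-180 sample (an assumption), n would be 140 or 120. Power at 0.80 per SD would then be 66% against 48%, or 60% against 42%. The rate ratios per SD are assumptions; the documents give none.

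**5. Choice of cut.** This was simulated with no true effect, 4,000 data sets, mean 1.2, k = 0.4 and n = 148. The false-positive rate was 5.5% for continuous titer and 5.8% for a median split. Testing nine cuts between the 20th and 80th percentiles against the outcome and keeping the best gave 22.6%. A repeat simulation gave 22% at both n = 148 and n = 175.

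**6. The reverse case.** If the true effect is a step exactly at a median cut (rate ratio 0.65, n = 150, mean 1.4, 1,500 runs), power is 71% for the split and 52% for linear log titer.

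**The case against.** The strongest reply is that this is one exploratory objective, that log-linearity is as much an assumption as a threshold, and that a split wins if there is a step at the cut (step 6). All of that is true. It argues for low severity and for checking the shape of the relation. It does not favour an unspecified split, because the protocol names no threshold at which a step would be expected.

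The effect sizes also deserve caution. For normal log titer, 0.80 per SD means a rate ratio of about 0.70 between the upper and lower halves (0.80 to the power 1.596, the distance in SD between the half means). That is stronger than the 0.75 the trial is powered to detect between vaccine and placebo. At 0.90 per SD the halves differ by about 0.85, and the analysis is weak whichever model is used.

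A reader might infer that choosing the cut after seeing the titers inflates the false-positive rate. It does not, so long as outcomes play no part: a median split is itself taken from the observed titers, and it held at 5.8%. The 22-23% figure describes a search against outcomes, which the text leaves possible but does not plan.

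Nor is this the plan's only dose-response question, since Section 3.2.3 also explores one, two and three doses received.

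The most serious limitation remains under either model. Sera are drawn on days 173-187 (Section 12). On the standard schedule, surveys start on day 10-14, so the 26th falls on day 185-189 (25 × 7 = 175 days later). Most episodes therefore precede the titer meant to explain them.

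**Conclusion.** The point holds as a low-severity improvement to a tertiary analysis. Section 3.2.3 plans a two-group split with no cut-off, and no continuous analysis is described. The announced SAP is not said to cover tertiary objectives.

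Under a log-linear effect and roughly normal log titer, the split loses at least about 36% of the information. At an assumed 0.80 per SD, that costs about 19 to 20 percentage points of power, at either sample size. At 0.90 per SD it costs only 6 to 7 points, from an already low base.

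Two stronger readings are not supported. The set cannot be called fewer than 150 as a matter of record, because Section 3.2.5 implies about 175. And the primary conclusion is not at risk, because the primary analysis does not use titers.

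**What to change.** In Section 3.2.3, replace the high/low comparison with the following:
- Among vaccinees with a day-180 titer, fit the Section 14 negative binomial model with log2 RVNA concentration as a continuous term and log weeks of observation as the offset.
- Report the rate ratio per doubling of titer with its 95% confidence interval.
- Assign one fixed, pre-stated value to results below the assay limit.
- Add a quadratic term as a check on log-linearity.
- Keep any high/low table descriptive, with its cut fixed in advance.

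Separately, reconcile the ancillary study size in Section 3.2.5 with the enrollment rate in Section 8, and state how many vaccinees are expected to have a day-180 titer.

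The cost is wording only: the sera, assay and model family stay the same. The price is the log-linear assumption, and lower power than a split if the true effect is a step at the cut. The change does not address the timing of the titer, which should be stated as a limitation of this analysis.
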